#### 8.2 Background Characteristics

Background characteristics will be summarized separately for Part A, and for the combined Part B and Part A/B Cohort 8. Summary tables will be presented by cohort and overall.

#### 8.2.1 Subject Disposition

#### Part A:

The number of subjects in the following categories will be summarized:

- Enrolled
- Enrolled and dosed (Safety Set)

The number and percentage (based on the Safety Set) of subjects in each of the following disposition categories will be summarized:

- Last Treatment Visit completed (Day 1, Day 2, Day 3, Day 4, and Day 5).
- Completed treatment
- Prematurely discontinued the treatment and the reason for discontinuation
- Completed study

• Prematurely discontinued the study and the reason for discontinuation

#### **Combined Part B and Part A/B Cohort 8:**

The number of subjects in the following categories will be summarized:

- Enrolled
- Enrolled and dosed (Safety Set)
- FAS

The number and percentage (based on FAS) of subjects in each of the following disposition categories will be summarized:

- Last Treatment visit completed (Day 1, Day 4, Day15/Week 2, Week 4, Week 8, Week 12, Week 18 and Week 24).
- Completed treatment
- Prematurely discontinued the treatment and the reason for discontinuation
- Completed study
- Prematurely discontinued the study and the reason for discontinuation
- Enrolled in a rollover extension study

A listing will be provided for subjects who discontinued treatment or who discontinued study with reasons for discontinuation.

#### 8.2.2 Demographics and Baseline Characteristics

Demographics, medical history and baseline characteristics will be summarized for Part A, and combined Part B and Part A/B Cohort 8, respectively, based on the Safety Set.

Demographic data will include the following:

- Age (in months)
- Sex (female and male)
- Ethnicity (Hispanic or Latino, not Hispanic or Latino, and not collected per local regulations)
- Race (White, Black or African American, Asian, American Indian or Alaska Native, Native Hawaiian or Other Pacific Islander, not collected per local regulations, and Other)

Baseline characteristics will include the following:

For the combined Part B and Part A/B Cohort 8 only, the following disease characteristics will also be summarized:

- Age at CF diagnosis
- Maternal/pregnancy history: complications in pregnancy, gestational age at delivery, method of delivery

- Does subject have abnormal liver function tests documented since birth?
- Any use (yes or no) of the following medications from birth to screening will be assessed: inhaled tobramycin, inhaled aztreonam, inhaled colimycin, inhaled hypertonic saline, dornase alfa, ibuprofen, azithromycin, and pancreatic enzyme replacement therapy.
- Historical pancreatic test measurements

Medical history will be summarized by MedDRA system organ class (SOC) and preferred term (PT).

No statistical tests will be carried out to evaluate any baseline imbalance between dose groups.

#### 8.2.3 Prior and Concomitant Medications

Medications used in this study will be coded by using the World Health Organization Drug Dictionary Enhanced (WHO-DDE) and categorized as the following:

**Prior medication:** any medication that started before the first dose date of study drug, regardless of when the medication ended.

**Concomitant medication:** medication continued or newly received on or after the first dose date of study drug through the end of TE period.

Post-treatment medication (combined Part B and Part A/B Cohort 8 only): medication continued or newly received after the TE period.

A given medication may be classified as follows: prior, concomitant, post-treatment, both prior and concomitant, both concomitant and post-treatment, or prior, concomitant, and post-treatment.

If a medication has a completely missing or partially missing start/stop date and it cannot be determined whether it was taken before the first dose date, concomitantly, or after the TE period, it will be classified as prior, concomitant, and post-treatment.

Prior medications and concomitant medications will be summarized descriptively using frequency tables by preferred name.

For the final analysis, medications received during the period from the first dose of study drug through the end of Part A participation will be summarized as concomitant medications in Part A. A similar rationale will be adopted for concomitant medications in the combined Part B and Part A/B Cohort 8.

Summaries of medications will be based on the Safety Set.

Post-treatment medications will be listed by subject.

Details for imputing missing or partial start and/or stop dates of medication are described in Appendix B.

#### 8.2.4 Study Drug Exposure

Duration of study drug exposure (in days) will be calculated as: last dose date – first dose date + 1 day, regardless of study drug interruption.

Exposure summaries will be based on the Safety Set.

## 8.2.5 Study Drug Compliance (Combined Part B and Part A/B Cohort 8 only)

Study drug compliance based on the number of sachets taken will be calculated as:  $100 \times [(\text{total number of sachets dispensed}) - (\text{total number of sachets returned})]/(\text{total number of sachets planned to be taken per day} \times \text{duration of study drug exposure in days}).$  The maximum percentage of sachets taken will be 100%.

Note: For Part A/B Cohort 8 only, multiple sachets of 5.7 mg will be used to achieve doses of 11.4, 17.1, and 22.8 mg. Total number of sachets planned to be taken per day to achieve each dose is:

Doses (q12h) Total number of sachets of planned to be taken per day

5.7mg	2
11.4mg	4
17.1mg	6
22.8mg	8

Study drug compliance based on study drug exposure will be calculated as:  $100 \times [1 - (total number of days of any study drug interruption) / (duration of study drug exposure in days)].$ 

Study drug compliance will be summarized descriptively by the number of subjects (n), mean, SD, SE, median, min, and max. They will also be summarized in categories: <80% and  $\ge80\%$  using frequency tables.

Study drug compliance summaries will be based on the Safety Set.

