Medications and procedures review	Continuous from 28 days before the Screening Visit (or from birth, as relevant) through the ETT and Follow-up Visit (if required; see Section 10.3.1)										

CF: cystic fibrosis; ECG: electrocardiogram; ETT: early termination of treatment; ICF: informed consent form; [REDACTED]; OE: ophthalmologic examination; PK: pharmacokinetic; q12h: every 12 hours

^q Study drug will be administered q12h. Each dose of granules will be mixed with approximately 1 teaspoon (5 mL) of appropriate liquid or soft food (as listed in the study manual). Details of dose preparation and dose administration will be provided in the study manual. The dose administration dates and times, occurrence and time of regurgitation within 1 hour after dosing, and their timing with respect to food intake, will be recorded for the 2 doses prior to each PK clinic visit in each subject’s dosing diary. In addition, the time of administration of study drug and occurrence and time of regurgitation within 1 hour after dosing in clinic on the day of the visit will be recorded.

^r Week 12 and Week 18 Visits only. Study drug will only be dispensed at Week 24 to subjects enrolling in the open-label treatment arm of the Extension Study.

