13.5.2.4 Study Drug Exposure and Compliance

Exposure to study drug (i.e., duration of treatment) will be summarized for the Safety Set in terms of duration of treatment a subject received (in days).

Dosing compliance will be summarized for the Safety Set, and is calculated as the actual number of dosing occasions at which study drug was administered, as a percentage of the planned number of dosing occasions.

Duration of treatment and dosing compliance will be summarized by means of descriptive summary statistics.

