#### 8.2.6 Important Protocol Deviations/Violations

Important protocol deviations (IPD) are a subset of protocol deviations that may significantly impact the completeness, accuracy, and/or reliability of key study data or that may significantly affect a subject's rights, safety, or well-being. IPD rules will be developed and finalized before database lock.

The protocol deviations that should be considered as potential IPDs include, but are not limited to:

- Violation of subjects rights, safety or well-being
- Subject entered the study despite violation of any inclusion or exclusion criteria
- Subject was less than 80% compliant with study medications
- Subject received excluded concomitant medications
- Subject received the wrong treatment or incorrect doses
- Subject remained in study despite meeting withdrawal criteria

Occurrence of any of these events should be considered as potential IPDs, but the blinded team should categorize them as IPDs only if they have the potential to affect interpretation of study results.

IPDs will be presented as an individual subject data listing only.

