Table 11-2 Study VX15-770-124: Part B (Screening and Treatment Periods)

Screening Treatment Period Period (Day 1 to Week 24)									
Event/Assessment	Day -28 to Day -1	Day 1	Day 3	Week 2 (± 1 Day)	Week 4 (± 5 Days)	Week 8 (± 5 Days)	Week 12 (± 5 Days)	Week 18 (± 5 Days)	Week 24 a (± 5 Days)
In-clinic observation for 4 hours after administration of the first dose of study drug		X							
Study drug count		X		X	X	X	X	X	X
Study drug dispensing		X		X	X	X	X	X	Xr

Adverse events	Continuous from signing of ICF through ETT and Follow-up Visit (if required; see Section 14.1.1.3 of the Clinical Study Protocol)
Medications and procedures review	Continuous from 28 days before the Screening Visit through the ETT and Follow-up Visit (if required)

CF: cystic fibrosis; CFTR: CF transmembrane conductance regulator gene; ECG: electrocardiogram; ICF: informed consent form;

IRT: immunoreactive trypsin and/or trypsinogen; LFT: liver function test; PK: pharmacokinetic; q12h: every 12 hours

Study drug will be administered q12h. Each dose of granules will be mixed with approximately 1 teaspoon (5 mL) of liquid appropriate liquid or soft food (as listed in the study manual). Details of dose preparation and dose administration will be provided in the study manual. The dose administration dates and times, occurrence and time of regurgitation within 1 hour after dosing, and their timing with respect to food intake, will be recorded for the 2 doses prior to each PK clinic visit in each subject's dosing diary.

Study drug will only be dispensed to subjects enrolling in the open-label treatment arm of the Extension Study.

Table 11-3 Study VX15-770-124: Part B (Early Termination of Treatment Visit and Follow-up Period)

	Early Termination of Treatment Visit a	Follow-up Visit b	Follow-up Ophthalmologic Examination c
Event/Assessment	As Soon as Possible After the Last Dose of Study Drug	4 Weeks (± 7 Days) After the Last Dose of Study Drug	24 Weeks (± 14 Days) After the Last Dose of Study Drug
Clinic visit	X	X	
weight d	X	X	
Physical examination e	X	X	
Vital signs f	X	X	
12-lead ECGsg	X		
Serum chemistry and hematology h	X	X	
Ophthalmologic examination i	X		X
PK blood collection	X		
Study drug count	X		

Ad	dverse events	Continuous from signing ICF through the ETT (if required) and Follow-up Visit	Ocular adverse events only

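### The SAP's sachet compliance formula does not exclude Week 24 supply dispensed for the Extension Study, and the 100% cap would mask part of any resulting inflation

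*SAP*

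**What the plan says.** SAP 8.2.5 applies to Part B and Part A/B Cohort 8 combined. Its sachet measure has "total number of sachets dispensed" minus "total number of sachets returned" in the numerator, with no visit cut-off and no exclusion. The denominator is planned sachets per day times exposure days. SAP 8.2.4 counts those days from first to last dose, "regardless of study drug interruption". The result is truncated: "The maximum percentage of sachets taken will be 100" percent. SAP 8.2.5 also defines a second measure, based on days of interruption.

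The schedules of assessments mark dispensing at Week 24. For Part B, SAP Appendix A (Table 11-2) and Protocol Table 3-2 footnote it: "Study drug will only be dispensed to subjects enrolling in the open-label treatment arm of the Extension Study". For Cohort 8, Protocol Table 3-4 says: "Study drug will only be dispensed at Week 24 to subjects enrolling in the open-label treatment arm of the Extension Study". SAP Appendix A carries the same footnote for Cohort 8.

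SAP 8.2.6 lists as a potential important protocol deviation: "Subject was less than 80% compliant with study medications". It does not say which of the two compliance measures is meant. Protocol 13.5.2.4 defines compliance differently, as "the actual number of dosing occasions at which study drug was administered, as a percentage of the planned number of dosing occasions".

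**The concern.** The numerator and denominator cover different periods. A kit handed out at Week 24 to an infant entering the Extension Study treatment arm is for use after this study's last dose. Week 24 is the last treatment visit, and the Follow-up Visit is waived for these subjects (Protocol 9.1.3), so no later visit of this study can record the kit as returned. On the literal formula the whole kit counts as taken here, while the exposure days stop before any of it is used.

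Any such bias is selective. Subjects who stop early, or who complete and do not enter the treatment arm, receive no Week 24 kit. Two infants with the same adherence could therefore report different values in one table.

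The cap adds to the difficulty. A value above 100% is the ordinary warning that an accountability count is wrong or that more drug was used than planned, and this table cannot show one.

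At stake are the description of adherence and the count of subjects below 80%. Tables are by cohort and overall (SAP 8.1). The planned minimum is 5 subjects per Part B cohort and 6 in Cohort 8, so one infant crossing 80% moves a cohort's percentage by 1/5 = 20 points or 1/6 = 16.7 points at those sizes.

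**Working it through.** **The plan's own figures.** SAP 8.2.5 lists 2, 4, 6 and 8 planned sachets a day for 5.7, 11.4, 17.1 and 22.8 mg q12h. Taking (dose / 5.7) × 2 gives 1 × 2 = 2, 2 × 2 = 4, 3 × 2 = 6 and 4 × 2 = 8. These reproduce exactly.

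**Inputs.**
- Treatment period: 24 weeks × 7 = 168 days (both documents).
- Sachets per day: 2. The 25, 50 and 75 mg strengths are single sachets (Protocol synopsis), given q12h.
- Planned sachets: 168 × 2 = 336.
- Week 24 supply: not stated. I assume 2, 4 or 6 weeks. Six weeks is the longest gap between dispensing visits within this study (Week 12 to 18, and 18 to 24).
- All unused in-study sachets are assumed returned, and the Week 24 kit is assumed to be in this study's dispensing data.

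**Formulas.** For w weeks of supply, S = 14 × w sachets.
- Points added = 100 × S / 336.
- Reported value = min(100, true + points added).
- The reported value is below 80% only if true use is below 80 − points added.
- The cap truncates only if true use is above 100 − points added.

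| Assumed supply | S | Points added | True 75% reads | Below 80% only if true use is under | Cap truncates only if true use is over |
|---|---|---|---|---|---|
| 2 weeks | 28 | 8.3 | 83.3% | 71.7% | 91.7% |
| 4 weeks | 56 | 16.7 | 91.7% | 63.3% | 83.3% |
| 6 weeks | 84 | 25.0 | 100% | 55.0% | 75.0% |

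With the Week 24 kit excluded, true 75% reads 75% and stays in the below-80% category.

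**What the cap does and does not hide.** For a fully adherent rollover infant the raw value is 108.3%, 116.7% or 125%, and the table shows 100%. That figure happens to be right, but the signal that the count includes extra kits is lost. At lower adherence the cap is often not reached and the inflated value itself misleads. With 4 weeks' supply, true 60% reads 60 + 16.7 = 76.7%, uncapped and still below 80%, while true 70% reads 86.7%.

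**Apparent over-use.** Any raw value above 100%, for example 110% or 150%, is shown as 100%. The interruption-based measure is 100 × (1 − interruption days / exposure days) and also cannot exceed 100%. Neither compliance summary can therefore show use above plan.

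**The case against.** The strongest reply is that nothing shows the kits will be counted. Protocol Table 3-2 lets the Part B Week 24 visit double as Day 1 of the Extension Study, so the kit may sit in that study's records. The eCRF and its completion guidelines, on which the SAP rests, are not among the documents. A programmer could also reasonably read a measure of sachets taken, divided by this study's exposure days, as limited to this study's supply. This stands. The point is an unstated rule that two programmers could apply differently, not a demonstrated miscount.

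A reader might infer more than the documents support:

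- **That overdosing would go unseen.** It would not. SAP 8.2.6 lists incorrect dosing as a separate potential important deviation, and individual data are listed. A raw value above 100% may also mean only that sachets were lost or not returned.
- **That the protocol's dosing-occasion measure cures both problems.** It would not count Extension Study supply. But an infant given three sachets instead of two at every dose still has every occasion dosed, so it too reads 100%.
- **That this is the only evidence of drug delivery.** The SAP also has the interruption-based measure and exposure duration, and plasma concentrations are measured repeatedly (Protocol 12.3.1).
- **That very poor adherence would routinely pass as adequate.** Sachets are counted at scheduled visits, continued noncompliance is escalated (Protocol 11.9), and noncompliance is a ground for discontinuation (Protocol 10.4). Very low use sustained to rollover is unlikely.

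It is also true that no analysis set depends on compliance. The Full Analysis Set and Safety Set need only one dose, and there is no per-protocol set.

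**Conclusion.** The point holds as a conditional defect in SAP 8.2.5. Followed literally, the numerator admits supply for a period that the denominator excludes, because this study's own schedules contain the Week 24 dispensing and nothing removes it. If the kits are in this study's accountability data, sachet compliance for Extension Study treatment-arm subjects is raised by 8.3 to 25 points under an assumed 2 to 6 weeks' supply at 2 sachets a day. That is enough to move true 75% out of the below-80% category in every case shown. If the kits are recorded only in the Extension Study, this inflation is zero.

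The cap is a separate and smaller weakness. It removes the values above 100% that would expose such a count, or apparent over-use, in the sachet summary.

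The reach is limited to a descriptive table, and to the below-80% deviation flag if that flag uses the sachet measure, which SAP 8.2.6 leaves open. The safety, sweat chloride and PK results themselves do not change. The correction is still worth making, because it is specific, needs no new data and prevents an avoidable error in a reported number.

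**What to change.** Make two changes in SAP 8.2.5.

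1. Define dispensed sachets as those dispensed for use in this study, excluding any dispensed at Week 24 for the Extension Study.
2. Beside the capped summary, report the uncapped value or the number of subjects above 100%, with a footnote that such values may reflect unreturned sachets.

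The cost is two sentences of text, minor programming and the footnote. Some displayed values will exceed 100% for reasons unrelated to dosing, which is why the footnote is needed.

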#### 8.2.6 Important Protocol Deviations/Violations

Important protocol deviations (IPD) are a subset of protocol deviations that may significantly impact the completeness, accuracy, and/or reliability of key study data or that may significantly affect a subject's rights, safety, or well-being. IPD rules will be developed and finalized before database lock.

The protocol deviations that should be considered as potential IPDs include, but are not limited to:

- Violation of subjects rights, safety or well-being
- Subject entered the study despite violation of any inclusion or exclusion criteria
- Subject was less than 80% compliant with study medications
- Subject received excluded concomitant medications
- Subject received the wrong treatment or incorrect doses
- Subject remained in study despite meeting withdrawal criteria

Occurrence of any of these events should be considered as potential IPDs, but the blinded team should categorize them as IPDs only if they have the potential to affect interpretation of study results.

IPDs will be presented as an individual subject data listing only.

#### 8.3 Efficacy Analysis (Combined Part B and Part A/B Cohort 8 only)

Statistical methodology will be restricted to descriptive statistics only. All efficacy analyses described in this section will be based on the FAS, unless specified otherwise. Summary tables will be presented by visit for each cohort and overall, for combined Part B and Part A/B Cohort 8 based on the FAS.

#### 8.3.1 Analysis of Primary Efficacy Variable

Not applicable.

#### 8.3.2 Analysis of Secondary Efficacy Variable

The sweat chloride test is a standard diagnostic tool for CF, serving as a biomarker of *CFTR* activity. Collection of sweat samples will be performed at qualified study sites using an approved Macroduct® (Wescor, Logan, UT) collection device. Sweat samples will be sent to a central laboratory for testing and interpretation of results. Individual sweat test results will

[figure not shown]
not be disclosed to the study sites. Specific instructions for collection, handling, processing, and shipping of sweat chloride samples to the central laboratory will be provided separately.

[figure not shown]
Sweat chloride will be collected at visits as indicated in Appendix A. Absolute change from baseline in sweat chloride will be calculated as:  $\frac{mean(SW_{Left}, SW_{Right}) - SW_{Base}}{SW_{Right}}$ , where SWLeft and SWRight are the measurements obtained on the left and right arms, respectively, at a particular visit and SWbase is the mean of right and left baseline measurements. If 1 of the 2 measurements at a time point is missing, the other will be used as the mean. If both are missing, then sweat chloride is missing for that visit.

Note: A volume of  $\geq 15~\mu L$  is required for an accurate determination of sweat chloride. Any results reported having volume <15  $\mu L$  will not be included in analysis. In addition, sweat chloride with concentration >160 mmol/L will not be included in analysis.

Definition of Baseline: Only results obtained from sample collections completed prior to the first administration of study drug will be considered as baseline results. If sweat chloride collection was completed for 1 arm prior to the first dose and completed for the other arm after the first dose, the baseline will consist of a single measurement. If both sweat collections were completed after the first dose, the baseline sweat chloride result will be considered missing for analysis purposes.

Sweat chloride results (including changes from baseline) will be analyzed as a continuous variable using descriptive summary statistics and presented by visit.

#### 8.4 Safety Analysis

The overall safety profile of study drug will be assessed in terms of the following safety and tolerability endpoints:

- Adverse events
- Clinical laboratory values (hematology and serum chemistry)
- OEs
- Physical examinations
- Standard 12-lead electrocardiograms
- Vital signs

Safety endpoints will be analyzed based on the Safety Set, separately for Part A and for the combined Part B and Part A/B Cohort 8. Only a descriptive analysis of safety will be performed. Summary tables will be presented by visit for each cohort, and overall. All safety data will be presented in individual subject data listings. No statistical hypothesis testing will be conducted.

